After consenting, enrolled participants will be sent a link to complete an online baseline survey. Once the completed baseline survey has been returned, the participants will be sent a code or instructions to download the free app. They will also be sent a user/training manual for the AR app use. *Given that all participants will be motivated to quit smoking, basic cessation assistance will be provided, including Tobacco Free Florida’s Quit Tips smoking cessation manual and the FL state tobacco quitline phone number and website.* A few days after the app and quitting materials are sent, research staff will call participants to explain the materials and answer questions. Participants will be instructed to use the AR app over the next 7 days in locations and situations where they smoke (e.g., home, bar; see Figure 5), with the goal of at least 5 uses per day. Usage and rating data will be collected in real-time. After the 7-day app use period, participants will be sent a link to an online follow-up survey that includes feedback on the app, smoking within the prior 7 days and smoking cessation motivation. Within approximately 7-14 days of completing the 7 day app use, participants will complete a brief telephone interview with study staff on their perceptions of the app as a potential cessation adjuvant and cigarette use over the course of the study. Participants will be compensated with electronic gift cards with value totaling up to \$80. Participants will receive \$10 for each of the completed baseline and follow-up surveys and the follow up phone interview. Participants can also receive a bonus of \$5 for each online survey completed within 24 hours of being sent the link and a bonus of \$5 if the follow up phone interview is completed within 10 days of completing the app use period. Participants will also receive \$5 for each day that they use the AR app at least one time (for up to \$35). Participants must use the app on at least four occasions to be eligible for the follow-up survey and interview.

C.4.5. Measures

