To assess usability and acceptability, we will use both an established questionnaire, as well as questions developed for this study. Questions developed for this Aim are derived from [name] experience with implementing mHealth procedures among smokers, as well as the existing literature on usability testing (e.g., Harrison et al., 2013; Nayebi et al., 2012). We will also track how often participants use the app over the course of the week. The *System Usability Scale* measures participants’ perception of usability and learnability (Brooke et al., 1996; Lewis & Sauro, 2009). To assess other components of usability and acceptability, we will develop a questionnaire with Likert scale items to capture the following areas: *reality/co-existence* (same items as in Aims 1 and 2), *usefulness* (Would this app appeal to you if you were currently attempting to quit smoking?), *ease of use* (How easy/difficult did you find using the app?);, *ease of learning* (How many days did it take to get comfortable using the app?); and *satisfaction* (Would you recommend this app to a friend or family member to help them quit smoking?; Overall, how satisfied were you with the app?).

Participants will also be asked questions by a trained interviewer on their perceptions of the phone app as a potential adjuvant for smoking cessation. Specifically, participants will be queried with open-ended questions such as, “What type of changes would you make to the app to increase the likelihood of using it, or, to make it more enjoyable to use?; What features would you add to the app?; What was the easiest part of using the app?; What was the most difficult part of using the app?; What was the most interesting part of using

[figure not shown]

Figure 5: Simulated examples of AR stimuli in a smoker’s home setting, including a single stimulus (left) and a three-object compound stimulus (right).

the app?”. These interviews will be recorded, transcribed and coded for analysis (described in more detail in the Statistical Design attachment).

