The target sample size is not adequate for fully-powered tests of moderators or mediators. Nevertheless, we will conduct exploratory analyses attempting to identify potential influences on or boundary conditions of AR smoking cue-reactivity and extinction. Key theory-based moderators are sex, nicotine dependence, and cue-reactivity (self-reported via the WISDM subscale). For Session 2, cue-reactivity and reality/co-existence measures from Session 1 also will be evaluated. Each moderator will be tested individually using the interaction term in a regression model (e.g., Cue Type x Sex in Session 1 and Group x Sex in Session 2). For example, if sex were a small-medium moderator of extinction in Session 2 (i.e., $\beta \sim .2$), the current sample size provides Power = .67 to detect an interaction of Group x Sex. The key theory-based mediators will be the reality/co-existence measures within the same session. Mediation will be tested using methods developed by Preacher and Hayes (e.g., 2008a, 2008b).

Aim 3.

For Aim 3, we will calculate descriptive statistics to examine a priori benchmarks regarding the usability and acceptability of the app. If any of these benchmarks are not achieved, the app will be adjusted accordingly and re-tested in additional field studies (beyond the present proposal). *For motivation to quit, self-efficacy for quitting, smoking urge, and quit status, we will also derive descriptive outcomes. Given the small sample size, we will not be powered to detect significant changes over time. Nonetheless, we will examine these data for*

trends in the expected directions (e.g., increases in motivation and self-efficacy). Smoking status will be collected post-app testing to determine what percentage of the sample successfully quit smoking. A priori benchmarks for each measure are presented in Table 1.

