Qualitative analysis of interviews will be conducted. Interviews will be audio-recorded and verbatim transcripts created for content analysis (Charmez, 2006). Using hand coding, the goal will be to identify key themes/textual units related to the phone app. Content analysis will be conducted using an “intuitive” or “immersion/crystallizing” analysis plan, whereby the researcher reviews all data and pulls out those aspects most relevant to the research questions (Sandelowski & Barroso, 2003). The research team will identify key themes as they read through the interview transcripts. These findings will supplement quantitative data in order to identify potential changes/improvements for future iterations of the app.

Item	Scale	A Priori Benchmark
Usability and Acceptability Outcomes		
Daily use	From real-time data	≥ 80% of participants will use the app on ≥ 80% of days
System Usability Scale	Likert	≥ 80% will “strongly agree” that the app is usable (i.e., ratings ≥ 4 on 5-point scale)
Reality/co-existence	Likert	≥ 75% will rate these variables as ≥ 8 on 10-point scale
Usefulness	Dichotomous (Y/N)	≥ 75% will respond “yes”
Ease of Use	Likert	≥ 75% will indicate the app was easy to use
Ease of Learning	Days to learn (ratio); Dichotomous (Y/N)	≥ 75% will indicate 1-3 days for learning to use the app; ≤ 30% will contact staff for additional help using the app
Satisfaction	Dichotomous (Y/N); Likert	≥ 75% would recommend the app; ≥ 75% will indicate being very satisfied
Smoking Behavior		
Motivation to Quit	Contemplation Ladder/ARME	≥ 80% of the sample will increase on motivation to quit smoking
Cessation Self-Efficacy Scale	Likert Scale	≥ 80% of the sample will increase on self-efficacy for quitting
Urge to Smoke	Likert	≥ 75% of the sample will have lower urges to smoke in the last 2 days of app testing, when compared to the first 2 days of app testing
Smoking Abstinence	Dichotomous (Y/N)	None. Collected for descriptive purposes only.

Table 1. Benchmarks of Aim 3 Usability and Acceptability Testing.

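### Aim 3 surveys and interviews only participants with at least four app uses, and Table 1 does not say what its percentages are taken over

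*Combined protocol and SAP*

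**What the plan says.** C.4.3 plans 50 participants for Aim 3. Under C.4.4 the app goes out only after baseline: "Once the completed baseline survey has been returned, the participants will be sent a code or instructions to download the free app". Participants then use it for 7 days "with the goal of at least 5 uses per day". An online follow-up survey and a telephone interview come next, under this rule: "Participants must use the app on at least four occasions to be eligible for the follow-up survey and interview".

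The survey carries feedback on the app, recent smoking and motivation. C.4.5 adds the usability and acceptability questionnaires and pre/post measures of motivation and self-efficacy, and names no other post-app collection point for them. One interview question begins "What type of changes would you make to the app to increase the likelihood of using it". App usage, and the urge rating made at each use, are captured by the app itself.

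Table 1 sets the benchmarks. The daily-use row reads "≥ 80% of participants will use the app on ≥ 80% of days", the motivation row "≥ 80% of the sample will increase on motivation to quit smoking" and the ease-of-use row "≥ 75% will indicate the app was easy to use". The first speaks of participants, the second of the sample, and the third names no base. Neither Table 1 nor the Aim 3 part of Statistical Design and Power defines these terms or says how someone without a survey is counted. Missing any one benchmark leads to adjustment of the app, with re-testing left to later studies outside this proposal.

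**The concern.** Access to the acceptability questions depends on app use, which is itself a Table 1 usability and acceptability outcome. A person who opened the app at most three times in a week, against a goal of five times a day, is informative about acceptability, yet is neither surveyed nor interviewed. The app's own data can show that this person stopped, but not why. No other section plans to ask, and the reason cannot be recovered once the study is over.

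The undefined base adds to this. Those enrolled, those sent the app and those surveyed can be three different numbers. A reader of the results could not tell which one a reported percentage describes, and the choice can decide whether a benchmark is met.

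**Working it through.** The plan gives no power or sample-size derivation for Aim 3, so there is no figure to reproduce. The check is arithmetic on the denominators.

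**Inputs from the documents.** N = 50 (C.4.3); goal of 5 uses a day for 7 days (C.4.4); threshold of four uses (C.4.4); benchmarks of 75% and 80% (Table 1).

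**Assumptions.** All 50 are sent the app; an occasion is a single use; everyone eligible answers; the base is those surveyed; k people have fewer than four uses. The documents give no k, so 1, 5 and 10 are shown.

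**1. Height of the bar.** Intended uses = 5 × 7 = 35, and 4/35 = 11.4%. The rule removes only people with 0 to 3 uses.

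**2. Rows affected.** System Usability Scale, usefulness, ease of use, days to learn, satisfaction, motivation and self-efficacy. Reality/co-existence is affected only if it is not rated in the app. Daily use and urge come from app data and do not pass through the rule, although the urge row needs ratings in both the first and the last 2 days. The part of ease of learning that counts requests for staff help need not come from the survey.

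**3. Minimum count that meets a row.** Among those surveyed it is the benchmark × (50 − k), rounded up. On 50 it is 0.75 × 50 = 37.5, so 38, or 0.80 × 50 = 40. In the worst case none of the k would have met the row; in the best case all would have.

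| Row | k | Minimum surveyed | Worst case on 50 | Best case on 50 |
|---|---|---|---|---|
| 75% | 5 | 34/45 | 34/50 = 68% | 39/50 = 78% |
| 75% | 10 | 30/40 | 30/50 = 60% | 40/50 = 80% |
| 80% | 5 | 36/45 | 36/50 = 72% | 41/50 = 82% |
| 80% | 10 | 32/40 | 32/50 = 64% | 42/50 = 84% |

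At these minimum counts the row still holds on 50 only if at least 4 of the 5 (38 − 34, or 40 − 36), or 8 of the 10 (38 − 30, or 40 − 32), would have met it.

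**4. Where the result can differ.** Only from the minimum count up to 37 (75% row) or 39 (80% row):
- k = 5: 34–37 of 45 (75.6–82.2%) and 36–39 of 45 (80.0–86.7%).
- k = 10: 30–37 of 40 (75.0–92.5%) and 32–39 of 40 (80.0–97.5%).
- k = 1: the single count 37 of 49 for a 75% row. An 80% row needs 40 of 49, which already meets 40 of 50, so there is no gap.

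**5. Items that need exposure.** Someone with no use cannot rate ease of use. If all k had no use, the sensible base for such items is 50 − k and the rule changes nothing. If all k had 1 to 3 uses, the base is 50 and the table above applies. Motivation and self-efficacy can be asked of all 50 either way.

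**6. Daily use.** 0.80 × 7 = 5.6, so 6 days are needed. At most three uses means at most 3 days, so every omitted person fails this row. On 50 it needs 40 successes and therefore fails at k of 11 or more. At k = 5 it passes only if 40 of the other 45 (89%) succeed, and at k = 10 only if all 40 do.

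**The case against.** A minimum-exposure rule is defensible. Questions on ease, learning and realism presuppose use, and four of 35 uses is a low bar. Many low-engagement users clear it and can still say what would make them use the app more. Daily payment for use and a staff call before the use week may keep the omitted group small, though the documents do not quantify this. The wording about participants and the sample can also be read as all 50 recruited. On that reading a person without a post-app score cannot count as increased, so the motivation and self-efficacy rows would be conservative. All of this stands as a limit on the size of the problem. It does not restore the missing reasons for non-use, and it does not settle the base.

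A reader might infer that the rule inflates the benchmarks, hides low uptake or eases the app's path to the later trial. The documents do not support this. They give no direction of bias: low use could reflect dislike, technical trouble or early quitting in a group recruited as ready to quit. Low uptake has its own row, untouched by the rule. Any single missed benchmark already triggers adjustment, so the rule alters that decision only if every other row passes; at k = 10 the daily-use row alone would nearly always trigger it. Table 1 is not a formal gate to the later trial.

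Counting people with no use as failures on items they could not answer would also score non-use twice, so that cannot be the main analysis.

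**Conclusion.** The point holds, at minor to modest weight. As written, the survey-based acceptability results and the interview themes are selected on app use, the reasons for near-non-use are not collected, and the percentages have no defined base. With those surveyed as the base, a row can be met while the share among all sent the app is as low as 68% (75% row) or 72% (80% row) at k = 5. These are worst cases: they assume that all 50 were sent the app and that none of the omitted would have met the row. In the best case no result changes. How many are omitted and which way they would answer are unknown. Aim 3 is descriptive and unpowered, so no error rate is at stake; what is affected is what the percentages mean and what the interviews can teach.

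**What to change.** - Send the online follow-up survey to every participant who was sent the app. Those with at least one use answer all items. Those with no use answer only the motivation, self-efficacy and smoking items, plus a short question on reasons for non-use.
- Report the numbers with 0 and with 1–3 uses.
- State the base of each Table 1 row: all sent the app for daily use, motivation and self-efficacy; all with at least one use for items that need exposure. The urge row needs its own statement, because it requires ratings in both time windows.
- Show the result among those with at least four uses beside each survey-based row, so that nothing planned is lost.
- A figure on all sent the app that counts missing data as not met may be added, labelled as a worst-case sensitivity only, because it scores non-use and technical trouble as poor usability.
- Interviews of those below four uses are optional.

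The cost is a short amendment and, at the rates in C.4.4, at most $10 + $5 = $15 per added survey: $75 at k = 5 and $150 at k = 10. An optional interview adds at most another $15 per person, plus staff time for interviewing, transcription and coding. The percentages may look less favourable.

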The 2x2 within-subject design for Session 1 will provide measures of urge to smoke and reality/co-existence (for AR only) for analysis. Smoking cue-reactivity will be computed for both the AR and the in vivo conditions by subtracting the average urge to smoke (1-10 scale) following smoking cues from the average urge to smoke following neutral cues; higher scores represent greater smoking cue-reactivity. Based on the existing literature (Carter & Tiffany, 1999), we expect in vivo smoking cue-reactivity equivalent to a Cohen's $d = 1.0$, a very large effect. In terms of urge to smoke, this approximates an average difference score of 2.0 units with a standard deviation of 2.0.

Support for the effectiveness of AR to generate smoking cue-reactivity will be evaluated in two ways. First, average AR smoking cue-reactivity will be tested against a minimal threshold of Cohen's $d = 0.5$ (i.e., expected 1 unit on the urge to smoke scale) using a single-sample t-test. Second, the equivalence of the AR and in vivo stimuli toward generating smoking cue-reactivity will be evaluated using two one-sided tests (TOST) for equivalence.

The 142 participants completing Session 1 will be randomly assigned to the extinction or control condition in Session 2. With an estimated attrition of 10%, 128 are expected to complete Session 2. One measure of extinction will be the difference in urge to smoke at Trial 27 from urge to smoke at Trial 2, such that more positive values represent greater extinction of AR smoking cue-reactivity. Extinction based on this measure will be evaluated using a between-groups t-test. In addition, growth curve modeling will be used to compare the trajectories of urge to smoke using each self-report during the presentation of stimuli with the hypothesis of a greater negative slope for the extinction condition. Finally, the secondary measure of latency to smoke following the extinction trials will also be evaluated using a between groups t-test.

Sample size was driven by the power required for Session 2. Power was estimated using PASS 15 (2017). With 128 participants in Session 2 (64 per condition), alpha = .05, and a two-sided test, Power will $\geq .80$ to detect a Cohen's $d \geq .50$ (a medium effect size) using the t-test. *A medium effect size is consistent with most of the existing cue-exposure treatment literature on cravings to smoke despite variations in population, types of cues (e.g., visual, audio, in vivo), number of exposures, massed or spaced exposures and number of participants. Cohen's $ds = .20, .45, .52, .75, 1.15$ for studies with reported effect sizes or with effect sizes that could be easily calculated for smoking urges (Niaura et al., 1999; Corty and McFall, 1984; Lowe et al., 1980; Kamboj et al., 2012; Unrod et al., 2014). Although an effect size was not reported, Collins et al. (2011) found significant reductions in cravings following repeated cue exposure despite having a substantially smaller sample size ($N = 42$). Studies that did not find an exposure effect were severely underpowered with Ns ranging from 7 to 32 (Götestam & Melin, 1983; Raw & Russel, 1980; Lee et al 2004; [name] et al., 2012; Miranda et al. 2008; and LaRowe et al. 2007).* Growth curve modeling of urge to smoke will have greater power presuming reliable measurement. The 142 participants completing Session 1 will yield power $> .95$ to detect a small-medium ($d = .35$) AR smoking cue-reactivity effect that is greater than the minimal threshold (1 scale unit, $d = 0.5$). This N will also yield power $> .80$ using TOST with alpha = .05 to detect an average AR reactivity within 0.25 standard deviations of the average in vivo reactivity (expected 2 scale units, $d = 1.0$).

The target sample size is not adequate for fully-powered tests of moderators or mediators. Nevertheless, we will conduct exploratory analyses attempting to identify potential influences on or boundary conditions of AR smoking cue-reactivity and extinction. Key theory-based moderators are sex, nicotine dependence, and cue-reactivity (self-reported via the WISDM subscale). For Session 2, cue-reactivity and reality/co-existence measures from Session 1 also will be evaluated. Each moderator will be tested individually using the interaction term in a regression model (e.g., Cue Type x Sex in Session 1 and Group x Sex in Session 2). For example, if sex were a small-medium moderator of extinction in Session 2 (i.e., $\beta \sim .2$), the current sample size provides Power = .67 to detect an interaction of Group x Sex. The key theory-based mediators will be the reality/co-existence measures within the same session. Mediation will be tested using methods developed by Preacher and Hayes (e.g., 2008a, 2008b).

Aim 3.

For Aim 3, we will calculate descriptive statistics to examine a priori benchmarks regarding the usability and acceptability of the app. If any of these benchmarks are not achieved, the app will be adjusted accordingly and re-tested in additional field studies (beyond the present proposal). *For motivation to quit, self-efficacy for quitting, smoking urge, and quit status, we will also derive descriptive outcomes. Given the small sample size, we will not be powered to detect significant changes over time. Nonetheless, we will examine these data for*

trends in the expected directions (e.g., increases in motivation and self-efficacy). Smoking status will be collected post-app testing to determine what percentage of the sample successfully quit smoking. A priori benchmarks for each measure are presented in Table 1.

Qualitative analysis of interviews will be conducted. Interviews will be audio-recorded and verbatim transcripts created for content analysis (Charmez, 2006). Using hand coding, the goal will be to identify key themes/textual units related to the phone app. Content analysis will be conducted using an “intuitive” or “immersion/crystallizing” analysis plan, whereby the researcher reviews all data and pulls out those aspects most relevant to the research questions (Sandelowski & Barroso, 2003). The research team will identify key themes as they read through the interview transcripts. These findings will supplement quantitative data in order to identify potential changes/improvements for future iterations of the app.

Item	Scale	A Priori Benchmark
Usability and Acceptability Outcomes		
Daily use	From real-time data	≥ 80% of participants will use the app on ≥ 80% of days
System Usability Scale	Likert	≥ 80% will “strongly agree” that the app is usable (i.e., ratings ≥ 4 on 5-point scale)
Reality/co-existence	Likert	≥ 75% will rate these variables as ≥ 8 on 10-point scale
Usefulness	Dichotomous (Y/N)	≥ 75% will respond “yes”
Ease of Use	Likert	≥ 75% will indicate the app was easy to use
Ease of Learning	Days to learn (ratio); Dichotomous (Y/N)	≥ 75% will indicate 1-3 days for learning to use the app; ≤ 30% will contact staff for additional help using the app
Satisfaction	Dichotomous (Y/N); Likert	≥ 75% would recommend the app; ≥ 75% will indicate being very satisfied
Smoking Behavior		
Motivation to Quit	Contemplation Ladder/ARME	≥ 80% of the sample will increase on motivation to quit smoking
Cessation Self-Efficacy Scale	Likert Scale	≥ 80% of the sample will increase on self-efficacy for quitting
Urge to Smoke	Likert	≥ 75% of the sample will have lower urges to smoke in the last 2 days of app testing, when compared to the first 2 days of app testing
Smoking Abstinence	Dichotomous (Y/N)	None. Collected for descriptive purposes only.

Table 1. Benchmarks of Aim 3 Usability and Acceptability Testing.

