If, at the beginning of either session, a participant self-reports smoking within the past 3 hours, s/he will be rescheduled. *Further, smoking status will be assessed at the beginning of Session 2; any participant who indicates that s/he has quit smoking for 24 hours or more will be ineligible for Session 2 (as participants will be asked to smoke during this session).* Otherwise, participants will then complete each respective session as described below. Participants will complete all procedures in a private laboratory room at TRIP. The procedures will be video-recorded from a central control room. The recordings will be reviewed to confirm study fidelity, and they will be used to score latency to smoke after Session 2.

C.3.5. Randomization

Session 1 will utilize a 2 x 2 within-subject design. Session 2 participants will be randomly assigned to either the extinction or control condition after stratifying by sex and cigarettes per day (cut point = 10). Block size will be 8 given the target sample size of 64 per condition (see below) and the 4 stratification cells.

C.3.6. Lab-based sessions: Descriptions of AR and In Vivo Cues

[figure not shown]
C.3.6.a. *AR Cues.* All AR cues will be presented via a smartphone provided to participants during the lab session. Six AR smoking cues and six AR neutral cues will be presented to participants. Although these cues can be presented individually (e.g., a single cigarette), we will have the ability to combine cues (e.g., cigarette in an ashtray). Further, movement of components of the cues (e.g., smoke coming up out of a cigarette, ash falling) will also be utilized whenever possible. Finally, participants will be encouraged to move around the stimuli to interact with the cue, as AR allows for the individual to see a stimulus from various angles. Urge to smoke and reality/co-existence questions will appear on the smartphone screen with response options. The AR app will allow for experimenters to select the order of the cues, as described below.

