The extinction session will use only the AR cues (smoking and neutral). As noted above, participants will be randomized to either the extinction or control group. Twenty-eight trials of cues will be presented for each group. Both groups will receive the same neutral cue in Trial 1 (to establish baseline urge) and the same smoking cue in Trial 2 (for pre-test cue-reactivity). Then, the extinction group will receive smoking cues for trials 3-26, whereas the control group will receive neutral cues. Both groups will receive matched smoking cues for the second to last trial (27) followed by matched neutral cues for the final trial (28), for post-test cue-reactivity. Each cue will be presented for 1 minute and will be shown 4 times in trials 3-26. Figure 4 shows a visual representation of cue presentation for each group. With respect to the order of the cues, we will create 4 quasi-random orders for each condition (each comprising 4 blocks of 6 images, with no image repeated twice over a series of three images), which will be varied across participants. *We derived these procedures from the existing cue-exposure literature (e.g., Carpenter et al., 2009; Collins et al., 2011; Conklin & Tiffany, 2002; Kamboj et al., 2012; LaRowe et al., 2007; [name] et al., 2012), and although no specific guidelines exist, these studies typically exposed participants to cues for up to 60 minutes total (54 minutes in the current study); utilize one to nine cues (6 smoking and 6 neutral in the current study); and utilize various amounts of time for exposure to each individual cue, often ranging from 10 seconds to 5 minutes (1 minute in the current study). For this study, we wanted each cue to be presented multiple times to allow sufficient time and exposure for extinction to occur, which ultimately resulted in 28 trials.*

[figure not shown]

Figure 4: Session 2 Procedures
N = Neutral Cue; S = Smoking Cue; Dotted lines indicate paired cues

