Following each cue, participants will complete the single-item measure of urge (primary outcome). Following the final trial (28) for both groups, participants will be presented with one of their own cigarettes and asked to take at least one puff. Latency to smoke will later be determined (using time stamps on the video-recording) and used as a secondary outcome as a behavioral measure of smoking motivation (e.g., Ditre et al., 2010; Kovacs et al., 2014; Shiffman et al., 2013; Stevenson et al., 2017). TRIP is equipped with 8 “negative pressure” rooms, compliant with state law regarding indoor smoking for research purposes that allow for the efficient removal of smoke between participants. Session 2 is expected to last 1.25 hours for pre-Covid-19 participants, and 1.5 to 2.5 hours for post-Covid-19 participants.

C.3.9. Compensation and Retention

Pre-Covid-19 participants will be compensated for Session 1 (\$40) and Session 2 (\$50). Post-Covid-19 participants will be compensated \$60 for Session 2. To aid in retention, the following procedures will take place: reminder phone calls prior to all study visits, flexible scheduling for sessions, reminder cards, requiring a functioning phone number and home address to contact participants by phone or mail as needed, and obtaining the name, address, and phone number of at least 2 collaterals (i.e., relatives, friends) who can provide contact information for the participants, should we be unable to reach them during the study.

C.3.10. Additional Measures

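### The test that sized Session 2 is an unadjusted t-test on the change in urge; adjusting for Trial 2 urge and the stratification factors would generally give more power at no extra data cost

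*Combined protocol and SAP*

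**What the plan says.** Under Statistical Design and Power, Aim 2, the extinction outcome is a change score: "One measure of extinction will be the difference in urge to smoke at Trial 27 from urge to smoke at Trial 2", signed so that a larger value means more extinction. The test follows: "Extinction based on this measure will be evaluated using a between-groups t-test". No covariate is named. The same section says "Sample size was driven by the power required for Session 2" and bases that power on the t-test: 64 per condition, two-sided alpha .05, d of at least .50, power of at least .80.

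A growth curve model of all urge ratings is also planned, and the section adds that "Growth curve modeling of urge to smoke will have greater power presuming reliable measurement", without a figure. Urge is the primary outcome (C.3.8), but neither analysis of it is named as primary.

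On the design, C.3.8 states that "Both groups will receive the same neutral cue in Trial 1 (to establish baseline urge) and the same smoking cue in Trial 2". The arms receive different cues only from Trial 3, and "Both groups will receive matched smoking cues for the second to last trial (27"). Urge is rated after every cue. C.3.5 stratifies randomisation by sex and by cigarettes per day, cut at 10. Neither factor is in a main Session 2 analysis; sex appears only among the exploratory moderators.

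**The concern.** Trial 2 urge is measured before the arms diverge, on the same smoking cue in both arms, so it is a valid baseline covariate and is already collected. Subtracting it from Trial 27 urge uses that information with a fixed weight of 1, which is optimal only by coincidence.

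The t-test has almost no margin over 80% power, so at the design effect the chance of missing a real extinction effect is about 20%. Section C.5 makes Aim 2 a go/no-go step: without the hypothesised results the team would change the protocol, retest in new participants and, if necessary, defer Aim 3. A false negative would be costly, so precision available without further data is worth having.

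**Working it through.** **Inputs from the documents.** 64 per condition, two-sided alpha .05, d = .50, power of at least .80 (Statistical Design and Power, Aim 2).

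**Assumed.** The Trial 2/Trial 27 correlation, rho, and the SD ratio k = SD(Trial 27)/SD(Trial 2). The only urge SD given, 2.0, is for the Session 1 smoking-minus-neutral difference and supplies neither. The SD that standardises d is not stated; it is taken as the change-score SD, because the t-test is on that score.

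**1. The plan's figure.** Noncentrality = .50 × √(64/2) = 2.828. With 126 df and critical value 1.979, power is .801. The stated power reproduces.

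**2. Variance comparison.** With SDs s1 and s2:

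- change score: s1² + s2² − 2·rho·s1·s2
- ANCOVA residual: s2²(1 − rho²)
- difference: (s1 − rho·s2)², which is never negative and is zero only when rho·k = 1

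With equal SDs the ratio of ANCOVA to change-score variance is (1 + rho)/2.

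**3. Power at N = 128, equal SDs, Trial 2 covariate only.** ANCOVA uses d = .50/√((1 + rho)/2) with 125 df. The detectable effect at 80% power is .50 × √((1 + rho)/2), on the change-score SD.

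| rho | variance ratio | t-test | ANCOVA | detectable d |
|---|---|---|---|---|
| .3 | .65 | .801 | .936 | .40 |
| .5 | .75 | .801 | .900 | .43 |
| .7 | .85 | .801 | .861 | .46 |
| .8 | .90 | .801 | .841 | .47 |
| .9 | .95 | .801 | .821 | .49 |

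Estimating the coefficient inflates the variance by about 1 + 1/124, which lowers the ANCOVA column to .934/.898/.858/.838/.818. A simulation with 20,000 replicates gave .934, .896, .862 and .816 at rho .3, .5, .7 and .9, with the t-test near .80 throughout. Including the small-sample factor, about 86, 98, 110, 118 and 124 participants in total would give 80% power.

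**4. Unequal SDs.** The variance ratio is k²(1 − rho²)/(1 + k² − 2k·rho).

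- k = .75: ratio .46 to .56 for rho .3 to .9; power .96 to .985.
- k = 1.25: ratio .784, .893, .981, 1.00 and .95 at rho .3, .5, .7, .8 and .9; power .887, .844, .809, .801 and .821. At rho .8 there is no gain, because rho·k = 1.
- k = 1.5: ratio .964 at rho .5 and .998 at rho .7; power .815 and .802.

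**5. If d is on the raw urge SD instead (equal SDs).** The change score has d = .5/√(2(1 − rho)) and ANCOVA has d = .5/√(1 − rho²). Power goes from .660 to .837 at rho .3, .801 to .900 at .5, .952 to .976 at .7, and .993 to .997 at .8.

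**6. Other settings, under the assumptions of step 3 (rho .3/.5/.7/.8/.9).**

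- N = 145, if the 17 pre-Covid participants are analysed with the 128: .849 for the t-test against .960/.932/.900/.883/.866.
- d = .45, one of the effect sizes the power section lists: .714 against .880/.831/.782/.759/.736.

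**7. Stratification factors.** These help only if they predict Trial 27 urge beyond Trial 2 urge. In a check at rho .5, a stratum effect of 0.6 SD on urge level at both trials left the change-score standard error at .1763 with or without the stratum, because it cancels. A 0.4 SD effect on Trial 27 alone lowered the ANCOVA standard error from .1575 to .1534 once the stratum was included.

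**The case against.** The strongest objection is that nothing in the plan is wrong. The t-test is valid under randomisation, its power figure is right, and this is a proof-of-concept study. That stands, and it is why the point is a recommended improvement and not a correction.

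Second, the gain is unknown and may be small. Both ratings are the same item from the same person in one sitting, so a high correlation is plausible; at rho .8 to .9 with equal SDs the gain is 2 to 4 points, and for some SD ratios it is nil. This stands too. The guarantee of equal or smaller variance is a large-sample one: as rho approaches 1 with equal SDs, the small-sample figure is .798 against .801. If all three covariates are fitted and the two stratification factors predict nothing, the variance factor becomes 1 + 3/122 with 123 df, and step 3 becomes .930/.893/.852/.832/.812. The possible loss is thus a fraction of a point with one covariate and under one further point with three.

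Third, the growth curve model already uses all the ratings and is expected to have more power. It does not settle the matter. In Trials 3 to 26 one arm rates smoking cues and the other neutral cues, so a slope difference mixes extinction with cue content. Trials 2 and 27 are the only ones that compare the arms on a smoking cue.

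Fourth, the footnote to C.3.1 shows that participants had already been enrolled, so replacing the powered test needs a dated, reasoned amendment. That is fair and is reflected in the fix.

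**Conclusion.** The concern holds as an efficiency gap. The unadjusted t-test is valid and has its stated power of .801. ANCOVA on data already collected estimates the same group effect with equal or smaller large-sample variance. Under equal SDs, with d on the change-score SD and N = 128, the gain runs from about 13 points at rho .3 to 2 points at rho .9. It is larger if Trial 27 urge is less variable than Trial 2 urge, and can vanish if it is more variable. All these figures rest on an assumed correlation and SD ratio and cover the Trial 2 covariate alone. The documents do not allow any added benefit from sex and cigarettes per day to be quantified.

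**What to change.** In Statistical Design and Power, Aim 2:

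- Name as the primary Session 2 analysis an ANCOVA of Trial 27 urge on group, Trial 2 urge, sex and cigarettes-per-day stratum (cut point 10). Report the adjusted mean difference with its confidence interval.
- State whether the 17 pre-Covid participants are analysed with the 128. If they are, add a pre/post-Covid term.
- Keep the change-score t-test as a supportive analysis. The existing sample-size statement can stay as a generally conservative basis.
- Put the same stratification factors in the growth curve model.

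The cost is a paragraph of analysis-plan text and a few lines of code. Every covariate is already recorded or was used at randomisation. The change should be dated and justified, and made before Session 2 urge is compared between the arms.
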